6.2 Secondary Objectives

The secondary objective of the study is to evaluate the clinical safety and performance of JTIN by the three following endpoints, when the MD is used within the scope and according to the manufacturer IFU:

- Implant survival rate: percentage of not exchanged nails up to 1 year follow-up (safety);
- Bone union achievement (performance);
- Post-treatment fracture-free survival up to 1 year follow-up (performance)

These variables will be visually compared with data available on other devices on the market (state-of-the-art).

The sample size was calculated also to provide a significant sample for the evaluation of the following main performance endpoint: bone union achievement.

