11.1.10 Procedures for Reporting and Recording AE, SAE and Medical Device Deficiencies

The investigator will follow the standard clinical practice to record data in the medical file. He/she will follow the national applicable vigilance procedures for any applicable case of AE or incident, and the manufacturer instruction to report any MDDs or AE as appropriate.

In addition to the above-mentioned requirements, the investigator will also record the AEs and MDDs in the eCRF. For both cases the investigator, when reporting the event in the eCRF will describe:

- date of the event;
- treatment;
- resolution;

- whether or not it is Serious and
- whether or not it is related to the use of the investigational device and the related procedure

When applicable, the investigator should also provide any available information and diagnostic measurements (laboratory test, X-ray etc) related to the AE and store it in the eCRF.

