12.2.2 Evaluation of Efficacy

The first efficacy endpoint (Bone union achievement) will be analyzed reporting the number and the proportion of procedures with bone union achieved (Success) together with the relative 95% confidence interval.

The second efficacy endpoint (Post-treatment fracture-free survival) will be analyzed reporting the number and the proportion of procedures with fracture(s) occurred in the treated bone up to 1 year follow-up together with the relative 95% confidence interval.

The cumulative freedom from fracture will be also evaluated using Kaplan-Meier (KM) method, the degree of uncertainty will be expressed with 95% confidence limits (calculated per the method proposed by Greenwood) and a KM graph will be presented along with the number of case-at-risk at exact time points.

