15.6 DIAGNOSIS & X-RAY IMAGES BY PROCEDURE

This analysis will be performed on FAIS population.

The categorical variables to be described are, N and (%):

- OI Type Diagnosis (Type I / Type II / Type III / Type IV / Type V / Type VI / Type VII / Type VIII)
- OI Type Diagnosis groups. A new variable will be calculated according to the following criteria*:
 - Mild/Non-deforming (Type I);
 - Severe (Type IV; Type V, Type VI);
 - Highly Severe/Progressively deforming (Type III, Type VII, Type VIII)
 - Lethal (Type II);

*References: <https://www.niams.nih.gov/health-topics/osteogenesis-imperfecta> and <https://pmc.ncbi.nlm.nih.gov/articles/PMC4314691/#tbl1>.

- Treated bone (Femur / Tibia)
- Body side (Left / Right)
- Body side (Only Left / Only Right / Both). A new variable will be generated based on original variable body side. For procedures with only left, with only right and with both the variable “Treated bone (Femur / Tibia)” will be described separately.
- Intended use of JTIN for this case (Fracture treatment / Osteotomy fixation (e.g. for deformity correction, bone reinforcement) / Malunion treatment / Non-union treatment)
- Was in the bone another fixation device, before JTIN application? (Yes / No)
- Was a software used during pre-planning ? (Yes / No)
 - In case yes, Which software?
 - In case yes, What information you looked for on the software?
 - In case no, Is there a particular reason why a software was not used?
- Preoperative AP projection X-Ray
- Preoperative ML projection X-Ray
- Number of additional radiographic images to upload (1 / 2)

The descriptive statistic (Mean, SD, Median, Q₁, Q₃, Min, Max) will be shown for the following continuous variables:

- Time from date of fracture to Date of screening visit (calculated as Date of screening visit minus date of fracture)
- Time from date of fracture to surgery (calculated as date of surgery minus date of fracture)

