24.3 POST TREATMENT FRACTURE-FREE SURVIVAL

The categorical variables to be described are, N and (%) and Clopper-Pearson confidence intervals will be shown at 95.0% as well, for the overall population and for subgroups of patients defined according to OI Type Diagnosis (Mild/Non-deforming / Severe / Highly Severe/Progressively deforming / Lethal) as defined in section 15.6 of this document:

- Number of patients with fracture(s) occurred (variable: "Bone fracture during or after treatment" in adverse event description + confirmation that the bone with fracture is the same where there is the implant*) in at least one procedure
- Number of procedures with fracture(s) occurred (variable: "Bone fracture during or after treatment" in adverse event description + confirmation that the bone with fracture is the same where there is the implant*)

* A list, with confirmation for each AE that the "fracture" is on the same bone or not, will be provided from Sponsor in order to confirm if the bone with fracture is the same where there is the implant.

The descriptive statistic (Mean, SD, Median, Q₁, Q₃, Min, Max) will be shown for the following continuous variable, for the overall population and for subgroups of patients defined according to OI Type Diagnosis (Mild/Non-deforming / Severe / Highly Severe/Progressively deforming / Lethal) as defined in section 15.6 of this document:

- Time to free fracture from surgery (months), per procedure, considered at the first Adverse Event onset date in which variable: "Bone fracture during or after treatment" in adverse event description has been checked. Calculated as the first adverse event onset date with a "Bone fracture during or after treatment" minus date of surgery.

Kaplan-Meier analyses will be provided for Time to free fracture. The median and the 95%CI as well as the number of events and patients censored will be provided.

The number of patients at risk will be displayed.

Event: if "Bone fracture during or after treatment" in adverse event description is clicked (which first occurs).

Time: Time to free fracture from surgery, as has been defined above.

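### SAP 24.3 rests the treated-bone fracture count on a sponsor-supplied list with no stated investigator role, source or cut-off, and leaves location out of the Kaplan-Meier event

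*SAP*

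**What the plan says.** Protocol 6.2 makes this a secondary endpoint: "Post-treatment fracture-free survival up to 1 year follow-up (performance"). Protocol 12.2.2 restricts it to the bone that carries the nail, reporting "the number and the proportion of procedures with fracture(s) occurred in the treated bone up to 1 year follow-up" with a 95% confidence interval, and adds a Kaplan-Meier analysis.

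SAP 24.3 carries this out in two ways:

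- **Counts and percentages, with Clopper-Pearson intervals.** A patient or procedure has an event if the bone-fracture AE term was recorded and there is "confirmation that the bone with fracture is the same where there is the implant". A footnote says that a list with this confirmation for each AE "will be provided from Sponsor in order to confirm if the bone with fracture is the same where there is the implant".
- **Time to fracture and Kaplan-Meier.** The event is the bone-fracture term alone, if it "in adverse event description is clicked (which first occurs"). No confirmation of location is asked for.

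On data flow, Protocol 11.1.10 states that "the investigator will also record the AEs and MDDs in the eCRF". The items listed there are date, treatment, resolution, seriousness and relatedness; the fractured bone is not among them. SAP 15.6 describes the bone that was operated on, "Treated bone (Femur / Tibia"), and its side, but not the bone that later broke.

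**The concern.** Which bone broke, and on which side, is a clinical fact that the site holds with the radiographs. Protocol 14.6 requires eCRF data to come from source documents. For this endpoint the deciding item instead reaches the analyst as a list from the sponsor, and the SAP does not say what it is based on, whether the investigator agrees it, or by when it must be final.

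The sponsor has a stake in the result: Protocol 5.2 gives confirmation of the benefit/risk ratio and retention of the CE mark as the purpose of the study. An entry of not-same-bone takes the event out of the count and percentage. The assignment is not always trivial either: a patient may carry nails in several bones (Protocol 7.2) and have 1 to 4 procedures (Protocol 12.3), so both bone and side must be right. Even if every entry is correct, the result is easy to challenge when the plan does not show where the entries came from.

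A second problem lies in the same section. The percentage and the survival curve use different events, so they can disagree for reasons unrelated to censoring.

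**Working it through.** **1. Event definitions side by side**

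| Output | Event needed | Location confirmed? |
|---|---|---|
| Protocol 12.2.2, proportion | fracture in the treated bone | yes, by definition |
| SAP 24.3, patients N (%) and CI | AE term plus confirmation | yes, by the sponsor list |
| SAP 24.3, procedures N (%) and CI | AE term plus confirmation | yes, by the sponsor list |
| SAP 24.3, time to fracture | first onset of the AE term | no |
| SAP 24.3, Kaplan-Meier | AE term | no |

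The list can therefore change the counts and percentages but not the time-to-event results. The Kaplan-Meier analysis can count a fracture elsewhere in the skeleton as a failure. Protocol 12.2.2 does not repeat the treated-bone restriction in its Kaplan-Meier sentence, but presents that analysis as a further look at the same endpoint, so the restriction should carry over.

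**2. Denominators**

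The plan states no figure for the fracture endpoint. It plans 20 evaluable procedures and a 20% loss: 20 / (1 − 0.20) = 25, which reproduces its total. One procedure is 1/20 = 5.0 points or 1/25 = 4.0 points. The shift is this large only when the reclassified fracture was the sole confirmed fracture of that procedure, because each procedure counts once.

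**3. Plausible number of events**

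The literature range for repeat fracture in Protocol 11.1.6 is 11.11% to 37.29%.

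- n = 20: 0.1111 × 20 = 2.2 and 0.3729 × 20 = 7.5
- n = 25: 0.1111 × 25 = 2.8 and 0.3729 × 25 = 9.3

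**4. Sensitivity of the percentage**

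Clopper-Pearson limits, the method named in SAP 14: lower = Beta quantile (0.025; x, n − x + 1); upper = Beta quantile (0.975; x + 1, n − x). The event counts are assumptions placed near the ends of the literature range.

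| n | Events before | One reclassified | Two reclassified |
|---|---|---|---|
| 20 | 2: 10.0% (1.2 to 31.7) | 1: 5.0% (0.1 to 24.9) | 0: 0% (0 to 16.8) |
| 20 | 7: 35.0% (15.4 to 59.2) | 6: 30.0% (11.9 to 54.3) | 5: 25.0% (8.7 to 49.1) |
| 25 | 3: 12.0% (2.5 to 31.2) | 2: 8.0% (1.0 to 26.0) | 1: 4.0% (0.1 to 20.4) |
| 25 | 9: 36.0% (18.0 to 57.5) | 8: 32.0% (14.9 to 53.5) | 7: 28.0% (12.1 to 49.4) |

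The intervals overlap heavily, but the point estimate is what will be set against the literature, and a single entry moves it visibly.

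**The case against.** The strongest reply is that the text has the list coming from the sponsor and no more. A reader might infer that the sponsor decides location in place of the investigator. The documents do not say so. Protocol 14.6 foresees analysis by contracted vendors, and the sponsor may simply be passing on what the site reported. That stands, and this point does not claim otherwise. What remains is that the SAP gives the investigator no stated role.

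Other replies, and what is left of them:

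- **Safeguards exist.** Protocol 11.1.10 asks the investigator to store available diagnostics, X-rays included, in the eCRF, and Protocol 14.2 plans full source verification of secondary endpoint variables. It would be wrong to say that the evidence on location bypasses the eCRF. But no listed field holds the fractured bone, nothing says that verification extends to the list, and verification is a sponsor activity.
- **Removals would be visible.** SAP 23.1.1 reports AE descriptions by patient and procedure, SAP 23.1.4 lists every AE, and the Kaplan-Meier event count uses all recorded fractures. A gap would show. The reason for each exclusion would not.
- **The survival estimate is safe.** A reader might infer that each removal improves the Kaplan-Meier curve. As written it cannot.
- **Lack of blinding.** The study is open-label for the investigator too (Protocol 7.4.1). The sponsor differs in its stake, not in what it can see.
- **Exclusion can be correct.** Leaving out a fracture of another bone is what Protocol 12.2.2 requires, and location is a radiographic fact with little room for judgement. Agreed; this also makes it easy for the site to record.

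**Conclusion.** The point holds as a weakness in how the endpoint is determined. A sponsor-supplied list is the deciding confirmation for the fracture count and percentage, with no stated source, investigator role or cut-off before database lock. The same section applies a different event, without location, to time to fracture and Kaplan-Meier.

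The possible effect of one reclassified procedure is 5 points at n = 20 or 4 points at n = 25. This assumes that the planned numbers are reached and that the procedure had no other confirmed fracture. The event counts used above are hypothetical. Nothing in the documents shows that any fracture was or will be wrongly excluded, so the figures measure sensitivity and not bias. The endpoint carries no test or success threshold, and Protocol 6.2 plans only a visual comparison with other devices, so what is at stake is the credibility of a descriptive estimate. That the location item sits outside the eCRF is an inference from the separate list and the AE items in Protocol 11.1.10; the documents do not state it.

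**What to change.** In SAP 24.3:

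1. Replace the sponsor list with the investigator's eCRF entry of bone and side for every fracture AE, obtained by query from source documents and X-rays.
2. Verify that entry as an endpoint variable under Protocol 14.2, and freeze it before database lock.
3. Use the resulting treated-bone fracture as the single event for the counts and percentages, the time to fracture and the Kaplan-Meier analysis.
4. Show the all-fracture result beside it, and list each fracture not counted with the reason.

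The cost is a handful of data queries and a short SAP edit. The site already holds the images, and SAP 23.1.1 already produces the all-fracture counts.

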7.2 Subjects and Sites Numbers

This study will be conducted only on patients with a regular indication for JTIN as per IFU (no off-label use will be included): the nail is indicated for fractures, osteotomies, malunions and non-unions in femur and tibia in pediatric patients suffering from osteogenesis imperfecta. The JTIN is intended to be used in pediatric patients, older than 18 months.

This study includes only one site (monocentric) located in Paris, France. The site was chosen for this study due to the number of subject devices already implanted, and the wideness of the indications covered by the surgeries. The site was also positively evaluated by sponsor for the appropriate qualification and competency of the investigator and of the staff, and availability of facilities and equipment.

The enrollment objective for this study is of 20 evaluable cases (i.e. procedures, see paragraph "Determination of the Sample Size"). For the purposes of this study, a case is defined as one implanted JTIN nail in one treated bone. Each case can be evaluated and recorded from implantation to the last visit for this study (see "Visits and Assessments Schedule" table and "Procedure" paragraph) or up to implant removal if this happens before the last visit. For each case one eCRF record will be created (see "Subject Identifier" paragraph).

Therefore, a single patient at the clinical site can contribute for more than one case e.g.: a patient can have several JTIN each implanted in a different bone, or can have more JTIN implanted in the same bone but at different times.

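### The Kaplan-Meier fracture analysis omits the same-bone condition that the fracture counts require, so one endpoint can be reported with two different event totals

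*SAP*

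**What the plan says.** Protocol 12.2.2 analyses the second efficacy endpoint as the number and proportion of "procedures with fracture(s) occurred in the treated bone up to 1 year follow-up". Under the same endpoint it adds: "The cumulative freedom from fracture will be also evaluated using Kaplan-Meier (KM) method", with Greenwood 95% limits.

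SAP 24.3 turns this into three outputs.

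- **Counts of patients and procedures with a fracture.** These need the bone-fracture item in the adverse event description plus "confirmation that the bone with fracture is the same where there is the implant". A footnote attached to these two counts says that a list stating, for each event, whether the fracture "is on the same bone or not, will be provided from Sponsor in order to confirm" this.
- **Time-to-fracture variable.** This is the first onset date of an event with the bone-fracture item checked, minus the surgery date. It has no same-bone condition and no footnote mark.
- **Kaplan-Meier analysis.** The event occurs when the item "in adverse event description is clicked (which first occurs". The time line reads: "Time: Time to free fracture from surgery, as has been defined above". The requested summary is: "The median and the 95%CI as well as the number of events and patients censored will be provided".

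Protocol 7.2 sets the observation period for each nail: from implantation to the last study visit, "or up to implant removal if this happens before the last visit". SAP 24.3 does not repeat this.

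**The concern.** The counts and the curve describe one secondary performance endpoint but use different event rules. A programmer following SAP 24.3 literally would build two event sets, and the report could show a same-bone count next to a curve with more events.

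This can realistically happen. Protocol 5.1 says that fractures in osteogenesis imperfecta can occur in any bone. Protocol 11.1.1 defines adverse events regardless of their relation to the device. The sponsor's list would be unnecessary if the adverse event item already identified the bone.

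The literal rule works against the device in two ways. It adds nails whose only fracture is elsewhere, and it can move a true treated-bone event to the earlier date of a fracture in another bone. The descriptive time-to-fracture summary uses the same variable and has the same fault. Protocol 6.2 plans a visual comparison of these endpoints with other devices, so the extra events could carry into that comparison.

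There are two smaller gaps. Censoring is expected, because the number censored is requested, but no time is defined for a nail without a fracture. Also, the only survival estimate that SAP 24.3 names is the median, which may well not be reached within one year.

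**Working it through.** **1. Event rules side by side**

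| Output | Fracture item ticked | Same bone confirmed |
|---|---|---|
| Protocol 12.2.2, proportion | fracture occurred | yes (treated bone) |
| SAP 24.3, patient and procedure counts | yes | yes |
| SAP 24.3, time to fracture | yes, first onset | not required |
| SAP 24.3, Kaplan-Meier event | yes, first occurrence | not required |

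**2. Inputs**

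- 20 evaluable procedures and about 25 enrolled (Protocol 12.3). The inflation reproduces: 20/(1 − 0.20) = 25.
- Repeat-fracture range of 11.11% to 37.29% (Protocol 11.1.6), given without a time horizon.
- The documents give neither a planned fracture rate for this study nor a rate of fractures in other bones. I assume 1 to 3 nails whose only fracture is in another bone.

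**3. Size of the discrepancy**

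With n = 20 and complete follow-up, the curve ends at 1 − (treated-bone nails + other-bone-only nails)/20. Each other-bone-only nail therefore costs 1/20 = 5 percentage points. With 25 nails followed completely, the step is 1/25 = 4 points.

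The literature range gives 0.1111 × 20 = 2.2 and 0.3729 × 20 = 7.5 fractures, so I use 2 and 7.

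| Treated-bone fractures | Reported count (Clopper-Pearson 95%) | Same-bone freedom | Curve ends at, with 1 / 2 / 3 other-bone-only nails |
|---|---|---|---|
| 2 of 20 | 10% (1.2% to 31.7%) | 90% | 85% / 80% / 75% |
| 7 of 20 | 35% (15.4% to 59.2%) | 65% | 60% / 55% / 50% |

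In the last cell the curve reaches 50%, so a median would be reported although 65% of nails are free of a treated-bone fracture. With the same-bone rule in the event and the time, every cell in a row equals the same-bone freedom.

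**4. Is the median a useful summary once the same-bone rule is applied?**

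The median is reached only if the curve falls to 50% or below. With X the number of nails fractured, taken as binomial:

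- n = 20: P(X ≥ 10) = 0.000018 (0.002%) at 11.11%, and 0.172 (17.2%) at 37.29%.
- n = 25: P(X ≥ 13) = 0.00000056 (below 0.001%) at 11.11%, and 0.096 (9.6%) at 37.29%.

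This takes the literature range as a 1-year rate, treats nails as independent, and assumes no early censoring. Independence is a simplification, since Protocol 12.3 allows 1 to 4 procedures per subject.

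**The case against.** The best defence is that the Kaplan-Meier lines omit the condition without stating that other bones count. The sponsor's list covers each fracture event, so it may have been meant to apply throughout the section. The documents also do not settle which form item a fracture elsewhere would be entered under: the bone-fracture item comes from the manufacturer's list of possible device effects, and the form has a separate item for other events. The short endpoint wording in the Protocol synopsis and section 6.2 names no bone, and the Kaplan-Meier sentence in 12.2.2 does not repeat it. The curve is an additional analysis in a descriptive single-arm study with no test or success criterion attached, and its error runs against the device. Protocol 7.2 already ends observation, and Protocol 12.1 and 12.2.2 already ask for cumulative freedom with Greenwood limits.

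Much of this stands and limits the severity. The authors may well have intended the list to apply. The outputs diverge only if at least one ticked fracture lies outside the implanted bone. The number of such fractures is assumed, and the censoring and median points are minor. It does not remove the contradiction. The Kaplan-Meier event is stated explicitly, the same-bone condition is attached only to the counts, and nothing in either document supports an any-bone curve for this endpoint.

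**Conclusion.** The concern holds and should be fixed. SAP 24.3 gives a Kaplan-Meier event and time that can count and date fractures outside the treated bone, contrary to its own counts and to the proportion in Protocol 12.2.2. The effect is 5 percentage points of fracture-free survival per affected nail with 20 nails, or 4 with 25, under complete follow-up. The number of affected nails cannot be derived from the documents, and it could be zero. The endpoint is still correctly estimated by the same-bone proportion with its Clopper-Pearson interval. The fault is confined to the additional Kaplan-Meier analysis that the protocol requires and to the time-to-fracture summary. The undefined censoring time and the reliance on the median are smaller gaps in the same paragraph.

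**What to change.** In SAP 24.3:

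1. Define the Kaplan-Meier event as the first fracture that the sponsor's list confirms in the JTIN-treated bone. Base the time variable on the onset date of that fracture, for both the curve and the descriptive summary.
2. Censor nails without such a fracture at the earliest of nail removal, last contact, death or the 1-year visit, consistent with Protocol 7.2.
3. Report the Kaplan-Meier fracture-free probability at 12 months with Greenwood 95% limits, next to the same-bone proportion. Give the median only if it is reached.

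The cost is SAP wording and one data check. The same-bone list is already planned, and visit dates are used elsewhere in the SAP. SAP section 22 names only the reason for study exit, so confirm that the eCRF also holds the dates of nail removal, death and last contact.

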14 STATISTICAL ANALYSIS METHODS

The methods of analysis to be used for both objectives of the study and for description of the study variables are detailed below.

Quantitative variables will be described with measures of central tendency and dispersion: mean, median, SD (standard deviation), Q1 (first quartile) and Q3 (third quartile), minimum and maximum. Qualitative variables will be described using absolute and relative frequencies.

In the descriptive analysis of qualitative variables, two percentage columns will be presented, total percentage (%) and valid percentage (% valid), that are respectively, the percentage over the sum of valid responses plus missing values and the percentage over the total of valid responses.

Clopper-Pearson confidence intervals at 95.0% will be shown for the primary and secondary objectives.

For time-to-event variables (i.e. fracture free-survival) will be analysed using the Kaplan-Meier method. The median and the 95% CI as well as the number of events and patients censored will be provided. Error standard will be estimated per the method Greenwood (Greenwood, 1926). KM graphs will be presented along with the number of case-at-risk at exact time points.

Change in Gillette Functional Assessment Questionnaire from Screening to 1 year follow up will be analysed by means of descriptive statistics as a continuous variable. Comparisons will be performed by means of paired t-test (parametric) or Wilcoxon (non-parametric) depending on the distribution of the sample.

These tests will be used in all bilateral cases and with a level of significance of 0.05. In cases where a p-value less than 0.05 appears, it refers to the existence of statistical significance.

No imputation for missing data will be considered.

No adjustment for multiple comparisons will be performed.

Data will be analysed using SPSS v29.0 or later.

Interim Analysis: No interim analysis is planned.

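### SAP 24.3 defines the Kaplan-Meier time only for nails that fracture and gives no censoring time for the rest

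*SAP*

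**What the plan says.** SAP 24.3 first defines a descriptive variable, per procedure, "considered at the first Adverse Event onset date in which variable" for bone fracture has been ticked; the surgery date is subtracted from that onset date. The Kaplan-Meier specification then reuses it: "Time: Time to free fracture from surgery, as has been defined above". The event line counts the first ticked fracture item. It does not mention the check that the fracture is in the implanted bone, which the fracture counts in the same section require.

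For output, SAP 24.3 states: "The median and the 95%CI as well as the number of events and patients censored will be provided". It also promises the number of patients at risk. SAP 14 repeats the commitment ("The median and the 95% CI as well as the number of events and patients censored will be provided") and asks for cases at risk on the graph. SAP 14 further says: "No imputation for missing data will be considered".

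Protocol 12.2.2 asks for the proportion of procedures with a fracture in the treated bone and, in addition, cumulative freedom from fracture by Kaplan-Meier. Protocol 7.2 follows each case from implantation to the last visit "or up to implant removal if this happens before the last visit". Neither document states a censoring date for nails that do not fracture, are removed, are lost or are withdrawn.

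**The concern.** The time line and the promised output in SAP 24.3 do not fit together. A time that exists only when there is a fracture produces no censored cases, yet the section promises a count of them. A program that follows the time line exactly would discard rows with no time. It would then estimate time to fracture among nails that fractured, which is a different quantity from freedom from fracture.

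Fracture-free survival is one of two performance endpoints. Kaplan-Meier is the only planned fracture analysis that can account for incomplete follow-up. A literal run could also pass unnoticed, because it returns a finite, plausible-looking median. An analyst who does notice must choose a censoring date in an open-label, single-arm dataset with the outcomes already visible.

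**Working it through.** The documents give no Kaplan-Meier figure to reproduce. The plan's total of 25 procedures does reproduce: 20 / (1 − 0.20) = 25 (Protocol 12.3).

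**Inputs.** 25 procedures and 20% drop-out (Protocol 12.3). Repeat-fracture range 11.11% to 37.29% (Protocol 11.1.6), taken here as 1-year rates, which the protocol does not say. Fractures are assumed to be spread evenly over months 2 to 11. This gives 25 × 0.1111 = 2.8, about 3 fractures, and 25 × 0.3729 = 9.3, about 9.

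**1. Literal coding.** Only the d fractured nails have a time, and all are events. The product-limit estimate is the product of (1 − 1/r) for r = d, d−1, …, 1. The last factor is 0, so the curve ends at 0% whatever the dates, provided d is at least 1. With d = 0 there is no curve. The number at risk starts at 3 or 9 and the censored count is 0. The reported median, 6.5 months under the even spread, is just the median fracture time.

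**2. Unfractured nails censored at 12 months, no earlier loss.** The estimate is 1 − d/n, and the Greenwood standard error reduces to √(S(1−S)/n).

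| n | Fractures | 12-month estimate | SE (points) |
|---|---|---|---|
| 25 | 3 | 22/25 = 88% | √(0.88×0.12/25) = 6.5 |
| 25 | 9 | 16/25 = 64% | √(0.64×0.36/25) = 9.6 |
| 20 | 2 | 18/20 = 90% | 6.7 |
| 20 | 7 | 13/20 = 65% | 10.7 |

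The median is not reached in any of these.

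**3. Effect of the censoring date, 5 of 25 unfractured nails lost at 6 months.**
- 3 fractures (one before month 6): 24/25 × 18/19 × 17/18 = 85.9%, against 88% if the lost nails are placed at 12 months. Shift 2.1 points.
- 9 fractures (four before month 6): 21/25 × 11/16 = 57.8%, against 64%. Shift 6.2 points.

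**4. Same question with 20% lost uniformly over the year and a constant hazard.** For true 1-year rate p, the share of lost nails with a fracture seen before loss is 1 − p/(−ln(1−p)). Placing the remaining lost nails at 12 months gives 1 − (0.8p + 0.2 × that share).
- p = 0.25: share 0.131; 1 − (0.200 + 0.026) = 77.4%, against 75%. Shift 2.4 points.
- p = 0.3729: share 0.201; 1 − (0.298 + 0.040) = 66.1%, against 62.7%. Shift 3.4 points.
- p = 0.1111: share 0.057; 1 − (0.089 + 0.011) = 90.0%, against 88.9%. Shift 1.1 points.

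In every case the later date gives the more favourable estimate.

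**The case against.** A reader might infer that the SAP prescribes dropping unfractured nails, and that its rule on missing data forbids giving them a time. The documents do not support either reading. SAP 14 and 24.3 both promise censored and at-risk numbers, and Protocol 12.2.2 names cumulative freedom from fracture, so unfractured nails are meant to stay in. Giving a censored case its follow-up time is part of the Kaplan-Meier method that SAP 14 itself specifies; it is not imputation. Protocol 7.2 also already ends observation at the last visit or at implant removal.

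The consequence is limited too. The proportion with its confidence interval is the first-listed fracture analysis and is unaffected. The study is descriptive, with no threshold for this endpoint. Protocol 12.1 requires deviations from the plan to be documented in the report. The comparison in steps 3 and 4 uses a 12-month placement for lost nails that no passage proposes.

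All of this stands, and it confines the 0% result to literal coding. It does not close the gap. Protocol 7.2 describes the observation period without setting a censoring rule, does not spell out loss or withdrawal, and is not carried into SAP 24.3. The time line actually written there still covers fractured nails only.

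**Conclusion.** The point holds as a wrongly specified time variable with no censoring rule. The fall to 0% follows from literal coding whenever there is at least one fracture, and needs no assumption about rates or dates. It should not be read as what the sponsor intends.

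The realistic effect is the choice of censoring date. It is roughly 2 to 6 points on the 1-year estimate (2.1 to 6.2 with 5 of 25 nails lost at 6 months), and smaller when losses are spread evenly and fractures are few. Against standard errors of 6.5 to 9.6 points at 25 nails this is modest, but every shift runs in the device's favour if lost nails are carried to 12 months. These sizes rest on 20% loss, on reading the literature range as 1-year rates, and on the assumed fracture timing. The SAP should be corrected before the analysis is run.

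**What to change.** - Replace the time line in SAP 24.3 with: *Time from surgery to the first fracture confirmed to be in the bone with the implant (event); nails without an event are censored at the earliest of nail removal, study exit or last visit with AE assessment, and the 1-year follow-up.*
- Make the event line use the same same-bone confirmation as the fracture counts, so that the two cannot disagree.
- Report events, censored and at-risk numbers per procedure. The time is per procedure, while SAP 24.3 labels the censored and at-risk numbers as patients.
- Keep the onset-minus-surgery variable for the descriptive row only.
- Where no exit or removal date is recorded, use the last visit with AE assessment. SAP 22 lists reasons for study exit but no dates, so their presence in the eCRF should be checked.
- Reconcile the final-visit window before using that visit as the end point: SAP 21.1 gives 23-25 months, while the protocol schedule gives 1 year ± 1 month.

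The cost is a short SAP edit and one derived variable. There is a small downside: censoring at nail removal may be informative, and this should be noted when the curve is reported.
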